- Sustained ventricular arrhythmia requiring defibrillation or cardioversion.
- Sustained supraventricular arrhythmia requiring drug treatment or cardioversion (classified as either pre-existing or post-operative onset)
- Cardiac conduction abnormalities or sustained bradycardia requiring permanent pacemaker placement (includes all PPMs whether associated with a serious AE or not)

Pericardial Fluid Collection

Accumulation of fluid or clot in the pericardial space that requires surgical intervention or percutaneous catheter drainage. This event will be subdivided into those with clinical signs of tamponade (e.g., increased central venous pressure and decreased cardiac output) and those without signs of tamponade.

Pleural Effusion

Accumulation of fluid or clot in the pleural space documented by chest radiogram or chest CT that requires evacuation with surgical intervention, chest tube or pigtail placement or medical management such as diuresis.

Pneumothorax

Presence of gas in the pleural space, documented by chest radiogram or chest CT, which requires evacuation or prolongs the duration of chest tube drainage.

Hepatic Dysfunction

Liver injury **and** impaired liver function defined as:

- ALT \geq 3xURL *and* total bilirubin* \geq 2xURL (>35% direct), **or**
- ALT \geq 3xURL *and* INR** $>$ 1.5.

* Serum bilirubin fractionation should be performed if testing is available; if unavailable, measure urinary bilirubin via dipstick. If fractionation is unavailable and ALT \geq 3xURL and total bilirubin \geq 2xURL, then the event is still to be reported as an SAE.

** INR testing not required per protocol and the threshold value does not apply to subjects receiving anticoagulants. If INR measurement is obtained, the value is to be recorded on the SAE form.

Major Infection

A new clinical infection accompanied by pain, fever, drainage and/or leukocytosis that is treated by anti-microbial agents (non-prophylactic). A positive culture from the infected site or organ should be present unless strong clinical evidence indicates the need for treatment despite negative cultures. The general categories of infection are listed below:

Localized Infection

Infection localized to any organ system or region (e.g., mediastinitis) without evidence of systemic involvement (see “*sepsis*” below), ascertained by standard clinical methods and either associated with evidence of bacterial, viral, fungal or protozoal infection, and/or requiring empirical treatment.

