Six Minute Walk and Gait Speed Tests: Differences between groups in gait speed and the distances travelled during the 6MWT will be compared using the Wilcoxon Rank-Sum test. We will also assess the extent to which changes over time (in gait speed and distance walked) are related to other outcomes.

Additional echo parameters: RV function (normal, mildly impaired, moderately impaired, severely impaired, peak tricuspid annular velocity, TAPSE, RVFAC) at 12 and 24 months and pulmonary artery pressure at 12 and 24 months will be compared between groups. RV volume as assessed by 3D TTE at 12 and 24 months will be compared between groups. Continuous variables will be compared for between group differences using the Wilcoxon Rank Sum test, and the level of function by chi-squared test.

Quality of life: QOL will be measured using the KCCQ, SF-12, and EQ-5D. We will employ two approaches to the analysis of QOL. The first will be to base the analysis on longitudinal mixed effects models. These models would predict outcome from treatment group and time. The mixed modeling approach requires an assumption that patient dropout is ignorable in that the probability of dropping out at any time is related only to previously observed data. Of course, this assumption may not hold, and moreover it is

impossible to test robustly from the data at hand. An alternative approach we will also use, not subject to this criticism, will be to separate the data into strata defined by the time of death or dropout. We will then estimate a separate linear model, including a treatment effect, for the data in each stratum. This method, known as pattern-mixture modeling, is not sensitive to un-testable assumptions about the dropout mechanism because it models the data directly in strata defined by dropout time. The method of Wu and Bailey is an instance of pattern-mixture modeling.

Adverse Events: Differences in the incidence of individual AEs within 24 months post-randomization will be compared between randomization arms using Poisson regression. Ninety-five percent confidence intervals (based on the Poisson distribution) for the risk ratios for individual AEs for treatment with MVS and TV annuloplasty versus MVS alone will be computed.

NYHA classification: The distribution of NYHA at 12 and 24 months will be presented for each randomization arm and compared using a chi-squared test.

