6. STATISTICAL METHODOLOGY

6.1 General Principles

Study day will be calculated from the reference start date, and will be used to show the study days of assessments and events. Reference start date is defined as the date of randomization unless otherwise specified. In analyses of index length of stay, index ICU days, peri-operative (30 day) mortality, and peri-operative (30 day) readmissions the reference date is

the date of surgery. In the situation where the event date is partial or missing, study day, and any corresponding durations are to appear partial or missing in listings. If a missing event date, such as a discharge date for a hospital readmission, is necessary to calculate patient-time at risk, the missing event date will be imputed using the median length observed for similar events.

Continuous variables will be summarized using the following descriptive statistics: number of non-missing values, means, standard deviations, medians, interquartile range, maximum, and minimum. Categorical variables will be summarized using number of non-missing values, counts and percentages.

Rates of events will be calculated as the ratio of the total number of events recorded divided by the total patient-time. Total patient-time will be calculated by summing the time (in study time units, e.g., days, months or years) that patients were at risk for a specific event from the reference time point until either study exit or the end of the time period of interest. Rates and 95% confidence intervals will be reported.

Time-to-event variables will be summarized using the Kaplan-Meier method or, in the presence of competing risk, the Gray method (Gray, 1988).

For any variable measured at multiple points in time, change from baseline will be calculated as the difference between the value of the variable at a specific point in time (e.g. 1 year) minus the baseline value. Relative change from baseline will be calculated as the value of a parameter at a specific point in time minus the baseline value of the parameter divided by the baseline value of the parameter. Percent change will be calculated as the relative change multiplied by 100.

All hypothesis testing will be conducted at the 0.05 two-sided significance level unless otherwise specified. P-values will be rounded to three decimal places. P-values less than 0.001 will be reported as <0.001 in tables. P-values greater than 0.999 will be reported as >0.999.

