6.5.2.5 Serious Adverse Events

Differences in the rate of individual serious AEs, AV-Block requiring pacemaker implantation, and new-onset atrial fibrillation within 24 months post-randomization will be compared between randomization groups using Poisson regression. Ninety-five percent confidence intervals for the rate ratios for individual AEs for treatment with MVS and TV annuloplasty versus MVS alone will be computed.

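### New-onset AF can occur only once per patient, so the planned Poisson interval is too wide; the cost is power to detect excess AF, and it matters if AF risk is about 20% or more

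*SAP*

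**What the plan says.** SAP 6.5.2.5 (Serious Adverse Events) puts individual serious AEs and the two named safety endpoints under one method: "AV-Block requiring pacemaker implantation, and new-onset atrial fibrillation within 24 months post-randomization will be compared between randomization groups using Poisson regression". It then promises "Ninety-five percent confidence intervals for the rate ratios for individual AEs". It states no robust variance, dispersion term or first-event rule.

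The protocol's Adverse Events paragraph (Analyses of Secondary Endpoints) plans "Ninety-five percent confidence intervals (based on the Poisson distribution) for the risk ratios for individual AEs". It therefore points to a model-based interval, and it calls the quantity a risk ratio where the SAP calls it a rate ratio.

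SAP 6.1 defines the ingredients. "Rates of events will be calculated as the ratio of the total number of events recorded divided by the total patient-time". The denominator adds up each person's time "at risk for a specific event from the reference time point until either study exit or the end of the time period of interest". No stop at a first event is written.

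The protocol's Cardiac Arrhythmias definition classes sustained supraventricular arrhythmia by pre-existing or post-operative onset. For pacemakers it "includes all PPMs whether associated with a serious AE or not".

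**The concern.** Poisson regression suits events that can recur, where the variance of the count equals its mean. A patient can have AF of new onset once. A first permanent pacemaker for AV block is, in practice, also a single event. The number of affected patients in an arm is then binomial, and its variance is smaller than the Poisson variance by the factor 1−p. A model-based Poisson interval does not know this.

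The SAP treats comparable outcomes differently elsewhere. It uses a log-binomial model for the binary primary outcome (6.5.1.2), chi-squared tests for 30-day readmission (6.5.2.6), and a competing-risks model for reoperation (6.5.2.1).

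At stake is how well the trial can show an excess of AF with the added annuloplasty. AF is one of only two specific events listed by name as safety endpoints in SAP 5.2.5.

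**Working it through.** **Inputs.** 400 patients randomized 1:1, so 200 per arm (SAP 6.5.1.1); two-sided 0.05 (SAP 6.1); 24-month window (SAP 6.5.2.5). The documents give no rate, power or interval width for these endpoints, so risks of 2–40% are assumed.

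**Check on the sample-size input.** The only stated figure to reproduce is the primary endpoint's power of about 90% for 25% vs 12%. With 200 per arm the plain chi-squared test gives 92.0%. With the final critical value of 1.969 it gives 91.9%, and with 1.5% crossover in each arm as well, 90.2%. The figure reproduces.

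**Formula.** Suppose there is one event per patient and everyone is followed for 24 months. Patient-time is then equal per patient, the rate ratio equals the risk ratio, and event timing drops out. With d₁ and d₂ affected patients:

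- Poisson: SE(log ratio) = √(1/d₁ + 1/d₂)
- Binomial: SE(log ratio) = √((1−p₁)/d₁ + (1−p₂)/d₂)

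For equal risks the quotient is 1/√(1−p). Example at p = 0.30: d = 60 per arm, √(2/60) = 0.183 against √(2 × 0.70/60) = 0.153, and 1/√0.70 = 1.195.

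| Risk in both arms | Poisson SE | Binomial SE | Excess | True size of nominal 5% Poisson test |
|---|---|---|---|---|
| 2% | 0.707 | 0.700 | 1% | (too few events to judge) |
| 5% | 0.447 | 0.436 | 3% | 3.7% |
| 10% | 0.316 | 0.300 | 5% | 3.6% |
| 20% | 0.224 | 0.200 | 12% | 2.8% |
| 30% | 0.183 | 0.153 | 20% | 1.8% |
| 40% | 0.158 | 0.122 | 29% | 1.1% |

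Sizes come from 60,000 simulated trials per setting. The closed form 2Φ(−1.96/√(1−p)) gives 2.8%, 1.9% and 1.1% at 20%, 30% and 40%.

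**Power.** For 40% vs 30%, the Poisson test has about 37%. A binomial risk-ratio model has about 55%, and the chi-squared test 56%.

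**One illustrative data set:** 80/200 vs 60/200, ratio 0.40/0.30 = 1.33, log ratio 0.288.

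- Poisson: SE √(1/80 + 1/60) = 0.171; 95% CI 0.95–1.86; p = 0.092.
- Binomial: SE √(0.60/80 + 0.70/60) = 0.138; 95% CI 1.02–1.75; p = 0.038.

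**If patient-time stopped at the first event.** This is a different rule from the one written.

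- If events also fell close to surgery, affected patients would add almost no time. The ratio above would become (80/120)/(60/140) = 1.56, an odds ratio.
- Type I error at 20%, 30% and 40% risk would be 7.2%, 9.0% and 11.3% with 90% of events in month 1. With all events near surgery it would be about 7.7%, 9.4% and 13.1%.
- With a constant hazard it would be 4.6–5.1% for risks of 10–40%, which is about right.

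**The case against.** **The pacemaker comparison is barely touched.** This stands. At assumed risks of 2–10% the excess is at most about 5%. Power for 10% vs 2% is 93.4% by Poisson and 93.7% by a binomial risk-ratio model. At low risks much of the shortfall in size comes from the log-scale Wald approximation: at 10% risk the binomial model itself gives 4.4%, against 3.6% for Poisson. A reader might infer that the intervals for both endpoints are materially wrong. The documents give no rates that would support this for pacemaker.

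**A reader might also infer that the plan risks false alarms of harm.** The documents do not support that. It needs patient-time to stop at the first event, which rests only on the words at risk in SAP 6.1 against a written end at study exit or the end of the period. It also needs events clustered early, and no timing is given. Under the written rule the interval errs on the wide side.

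**High AF rates are assumed.** This stands. The protocol's arrhythmia definition requires clinical compromise and, for sustained supraventricular arrhythmia, drug treatment or cardioversion. Nothing in the documents says that risk reaches 20–40% under that definition.

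**One event per patient is inferred.** For new-onset AF it follows from the term, but SAP 6.1 counts all recorded events. Repeat records in one patient would push the variance the other way. This is a further reason to write the counting rule down.

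**The SAP does not rule out robust variance, and 6.1 lets an unsuitable method be replaced.** Both are true. But the protocol wording is model-based, and the 6.1 clause names neither trigger nor replacement, so the choice would fall during data analysis.

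**Conclusion.** The concern holds, mainly for new-onset AF. With one event per patient, near-complete follow-up and patient-time as SAP 6.1 writes it, the Poisson interval is too wide on the log scale by 1/√(1−p). Whether this matters in practice depends on the AF risk, which the documents do not give: below about 10% it can be ignored, and from about 20% upward the loss of power to show excess AF is material. The percentage excess depends on the event risk and not on the number at risk, so restricting AF to patients without prior AF does not change it, although power would fall for every method.

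The unwritten rules for counting events and stopping patient-time are part of the same problem, because the result depends on them. These are secondary safety endpoints with no stopping rule attached.

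**What to change.** In SAP 6.5.2.5 and the protocol's Adverse Events paragraph, for new-onset AF and AV block requiring pacemaker:

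1. Count the first event per patient.
2. Define the at-risk set for AF as patients without prior AF.
3. Estimate a 24-month risk ratio and risk difference with binomial or robust variance, for example the log-binomial model of SAP 6.5.1.2 or Poisson regression with robust variance.
4. Fix in advance that, where death or withdrawal makes follow-up incomplete, cumulative incidence with death as a competing event is used, in line with the competing-risks approach already planned for reoperation.
5. Reconcile the protocol's risk ratio with the SAP's rate ratio.

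Keep rates per patient-time for serious AEs that can recur.

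The cost is small: wording changes and one pre-set rule for incomplete follow-up, with the same data and software. The SAP's purpose section allows revision before data lock.

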6.5.2.6 Hospitalizations

Index hospitalization length of stay and days in Intensive Care: We will compare post-surgery hospital LOS and days spent in ICU between treatment groups, separately by region (North America and Germany). A Wilcoxon Rank-Sum test will be used to test for differences within each geographic subgroup.

Perioperative readmission by 30 days: The distribution of the incidence of all-cause readmission, cardiovascular readmission, heart failure readmission, and TR re-operation by 30 days post-surgery will be presented for each randomization arm and compared using chi-squared tests.

Hospital readmission by 2 years: Rates of all-cause hospitalizations and rates of

cardiovascular and heart failure specific hospitalizations, within two years of randomization will be compared using Poisson regression.

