For computing sample size, we assume that at two years post randomization, 25% of patients treated with only MVS will experience the primary composite endpoint. We believe a meaningful effect worth detecting is at least a 50% relative reduction to 12%, for patients undergoing TV annuloplasty in addition to MVS. A total of 400 patients, randomized with equal probability to each arm, provides approximately 90% power to detect such a difference. For simplicity, power is based on a 0.05 level two-tailed chi-squared test. The sample size takes account of a potential single interim analysis to be performed in addition to the final analysis, and a minimal (less than 3%) rate of crossover.

Randomization Design and Procedure

Patients will be randomized using a 1:1 allocation to TV annuloplasty plus MVS or to MVS alone. The randomization will be stratified by clinical center (i.e., a separate randomization scheme will be employed in each center) and by whether severity of TR is moderate or not. A random permuted block design will be employed, with blocks of size 2, 4, or 6 randomly chosen. Randomization will be implemented as described in Randomization Section.

Data Monitoring and Analysis

Methods of Analysis

The primary outcome of this trial is treatment failure defined as the composite of (1) death from any cause, (2) reoperation for TR, (3) presence of severe TR at two years post randomization or, for patients enrolled with less than moderate TR and annular dilatation, progression by two grades (i.e., from none/trace TR to moderate TR) at two years. The null hypothesis is that there is no difference in the probability of treatment failures at two years post randomization between patients randomized to undergo TV repair during MVS

compared to patients randomized to undergo MVS alone. The primary null hypothesis will be tested in an intent-to-treat analysis using a 0.05 level two-tailed normal approximation (Wald) test.

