5.2.6 Hospitalizations

- Index hospitalization LOS and ICU days
- All-cause readmissions and readmissions for heart failure and TR re-operation through the first 30 days following surgery and through 24 months post-randomization

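### Index length of stay and ICU days are compared only within North America and within Germany; no overall region-stratified comparison is prespecified

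*SAP*

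**What the plan says.** Both documents list the outcome once, for the whole trial: SAP 5.2.6 has "Index hospitalization LOS and ICU days", and the protocol's Endpoints section has the same line under Hospitalizations.

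The analysis is regional only. SAP 6.5.2.6 compares the arms in North America and in Germany separately, and then: "A Wilcoxon Rank-Sum test will be used to test for differences within each geographic subgroup". The paragraph on hospital stay and intensive care in the protocol's Analytical Plan gives the same rule. Neither text gives a pooled or stratified test, a combined estimate, a treatment-by-region interaction, or a way to read the two regional results together.

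Three other statements bear on this:

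- SAP 6.1 sets the level for each regional test: "All hypothesis testing will be conducted at the 0.05 two-sided significance level unless otherwise specified".
- SAP 6.1 also allows ad hoc analyses, but the SAP's Purpose section requires any analysis it does not name to be reported as unplanned. The same section allows SAP revisions before data lock.
- The LOS text gives no reason for the split. The nearest is in the protocol's Economic Measures section, which restricts the cost analysis to US centers partly because hospital practice differs between countries.

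**The concern.** A difference in discharge practice between regions is a good reason not to mix North American and German stays in one ranking. It is not a reason to do without an overall comparison. Randomization is stratified by clinical center, and each center lies in one region, so the arms are randomized within region. A rank test stratified by region compares patients only with others in their own region, so a regional difference in the level of stay cannot bias it, and it still uses every randomized patient.

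As written, the plan yields two answers to one question and no rule for joining them. If the effect is the same in both regions, the likely output is one significant and one non-significant regional result, which is easily misread as a regional difference. An overall test added later would carry a post hoc label.

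The plan is also uneven. In the same SAP section, readmission by 30 days and hospitalization rates over two years are compared across the whole trial, although they too depend on local practice.

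**Working it through.** **The plan's own figure.** The only power statement near this point is for the primary endpoint (protocol, Sample size): "A total of 400 patients, randomized with equal probability to each arm, provides approximately 90% power to detect such a difference". The rates are 25% and 12%. With 200 per arm and a pooled rate of 0.185:

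z = [0.13·√200 − 1.96·√(2·0.185·0.815)] / √(0.25·0.75 + 0.12·0.88) = 1.408, so power = 92.0%.

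With the final critical value 1.969 it is 91.9%. With 3% crossover in both arms (24.6% against 12.4%) and 1.969 it is 88.4%. The stated figure reproduces, but it concerns a binary outcome on all 400 patients and says nothing about LOS or ICU days.

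**Inputs for LOS.** From the documents: 400 patients, 1:1, two regions, two-sided 0.05, Wilcoxon tests. Assumed, because the documents give no value: a shift of d SD on a scale where stay is roughly normal (such as log days), the same d in both regions, and the regional split.

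**Formula.** With m patients per arm and Wilcoxon efficiency 3/π = 0.955:

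θ = d·√(0.955·m/2), power = Φ(θ − 1.96) + Φ(−θ − 1.96).

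For a common shift, θ² adds over regions, so the stratified test on all 400 has the θ for m = 200.

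**d = 0.3.** Stratified test: θ = 0.3·√95.5 = 2.932, power 83.4%, whatever the split. A region of 200: θ = 0.3·√47.7 = 2.073, power 54.5%. With regional powers p and q, both are significant with probability pq, and exactly one with probability p + q − 2pq.

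| Split | Larger region | Smaller region | Both significant | Exactly one |
|---|---|---|---|---|
| 200/200 | 54.5% | 54.5% | 30% | 50% |
| 250/150 | 64.0% | 43.5% | 28% | 52% |
| 300/100 | 71.9% | 31.1% | 22% | 58% |
| 360/40 | 79.4% | 15.3% | 12% | 70% |

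**d = 0.45.** Stratified test: θ = 4.397, power 99.3%. Regional power is 87.5% in each region (200/200) or 93.5% and 76.8% (250/150).

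**Simulation check.** Stays were drawn as rounded log-normal values (log-scale SD 0.5), 2,000 trials per setting, with splits from 200/200 to 360/40. For d = 0.287, where the formula gives the stratified test 80% power, simulated van Elteren power was 79% to 82%. With no effect it rejected in 4.5% to 5.2% of trials. When stays were 1.5 times as long in one region and the split was even, an unstratified Wilcoxon test had 74% power against 79.5% for van Elteren. So the overall test should be stratified, not simply pooled.

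**False positives.** With no effect, two independent tests at 0.05 give at least one significant region with probability 1 − 0.95² = 9.75% per outcome.

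**The case against.** The best defense is that regional analysis is a deliberate, prespecified choice. LOS partly measures discharge practice, and the protocol records discharge location for that reason or a similar one. If practice changes how much the added procedure lengthens stay, and not only how long patients stay in general, the regional answers are the meaningful ones, and the common shift assumed above is the very thing left open. That stands as a reason to keep the regional results. It does not explain having no overall result for an endpoint listed once for the whole trial.

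A reader might infer that the LOS analysis is underpowered. The documents do not support this in absolute terms. They set no power target, SD or effect for LOS or ICU days, and the regional tests do well if the effect is large. Only the relative statement holds: less power than the stratified test, if the shift is common.

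A reader might also assume that longer stay is a main expected cost of annuloplasty. The protocol's Rationale speaks only of the risk of an additional procedure, and cost has its own analysis without German data.

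Nor does multiplicity carry much weight. The SAP runs many secondary tests at 0.05 with no stated adjustment, so one more or fewer changes little.

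**Conclusion.** The gap is real and small. Both documents plan within-region tests only, and neither prespecifies an overall comparison of LOS or ICU days. Under a common shift, a stratified test is the more powerful choice: about 83% at 0.3 SD, against 31% to 72% for the regional tests when the split lies between 200/200 and 300/100. At 360/40 the larger region is close to the stratified test (79%), but the smaller has about 15%. These figures rest on the assumed shift, its being the same in both regions, and the assumed split.

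One further step is tempting: to rank in-hospital deaths as the longest stays. That would change the endpoint from days between surgery and discharge to a composite with death. Perioperative mortality is already analyzed separately, and the present point does not require the change. The primary endpoint, MACCE and the safety analyses are unaffected.

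**What to change.** In SAP 6.5.2.6, and in the matching protocol paragraph if it is amended, name a region-stratified Wilcoxon (van Elteren) test as the overall comparison of LOS and, separately, of ICU days. Because that test gives only a p-value, add a region-stratified combined estimate with a 95% confidence interval, for example a stratified Hodges-Lehmann shift, and state its scale. Keep the regional medians and within-region results, labeled as descriptive, and say that a significant result in only one region is not evidence of a regional difference.

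The cost is two or three sentences in the SAP and a little programming, with no new data. It must be done before data lock to count as planned. The downside is small: an overall test is most informative when the effect has the same direction in both regions, and the regional results will show whether it does.
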